## **Chinese Culture-Specific Intervention to Decrease the Stigma of Nursing Students towards Schizophrenia—A Pilot Randomized Controlled Trial**

### **Introduction**

Mental illness stigma does enormous damage to those with mental illness as well as their families, and the health care system (Brouwers, 2020). Schizophrenia is the most stigmatized disease among mental illnesses (Valery & Prouteau, 2020). In China, nearly 7.8 million people are diagnosed with schizophrenia, and 100,000 new diagnoses are recorded each year (Hu, 2018; Yao et al., 2013). The stigma of schizophrenia is mainly characterized by the stereotypes of danger, unpredictability, and a poor prognosis (Crisp, Gelder, Rix, Meltzer, & Rowlands, 2000). People with schizophrenia are widely considered as more dangerous and unpredictable than people with other mental illnesses (Reavley & Jorm, 2014).

In different cultures, people have different understandings of stigma meanings, treat it in different ways and yield different results (Yang, 2007). In China, some people believe that schizophrenia is caused by black magic or possessed or disturbed by spirits (gods or devils) (Tseng et al., 2013). Studies showed that socio-cultural and religious factors strongly affect stigmatizing attitudes (Waqas et al., 2020).

However, in China, few studies have been conducted with a focus on Chinese culture when it comes to decreasing mental illness stigma. China is a developing country with a culture of face-saving and Confucianism, totally different from western countries (Yang et al., 2014). Nurses play an essential role in all health care systems. When nursing students begin their nursing career, their attitude and behavior toward schizophrenia will affect the treatment and nursing of people with schizophrenia. A study showed that compared with medical students, nursing students hold even a more negative attitude towards people with schizophrenia (Taşkın et al., 2003).

In mainland China, fourth-year nursing students have finished their theoretical knowledge and then undertake clinical practice in the hospital prior to their graduation. Given the high prevalence of mental illness, such as schizophrenia, it is likely for the nursing students to meet some mental health consumers who require physical treatment and nursing care. Their stigma on consumers with schizophrenia will affect their delivery of quality healthcare and consumers' achievement of optimal health outcomes and prevent them from entering the mental health workforce after graduation. It is fundamental to address nursing students' stigma with appropriate intervention strategies.

There are three ways of decreasing mental illness stigma: protest, education, and contact with people who have a mental illness (Corrigan, Edwards, et al., 2001). The "contact" has superior efficacy and effectiveness in decreasing stigma as it may evoke an empathic emotional reaction (Tippin et al., 2019). Empathy is recognized as how an individual know other people's thinking and feeling and figure out what makes someone give a response to other people's suffering with sensitivity and care (Batson,

---

2009). It is found that improvement of empathy for the stigmatized group will be extended to a larger group of people with other mental illness (Batson et al., 2002;).

Besides, transformative learning can help individuals to transform their beliefs, assumptions, and experiences from new perspectives (Dincer & Inangil, 2021). It may develop nursing students' empathy and positive attitude towards people with schizophrenia. There are four transformative learning methods in education: investigative, collaborative, higher-order thinking, and interactive learning activities (Tsimane & Downing, 2020). To decrease nursing students' stigma towards schizophrenia, intervention methods should incorporate the transformative learning.

Knowledge-attitude-behavior practice (KABP) paradigm was used to guide researchers to develop intervention to decrease mental illness stigma (Foster, 2017;) as the lack of mental health knowledge and misconception of the fact will lead to stigma (Thornicroft, 2006). Thus, a good intervention framework should combine transformative learning and KABP paradigm.

Review of previous intervention studies in decreasing mental illness stigma show certain limitations. Studies showed that socio-cultural and religious factors strongly affect stigmatizing attitudes, but seldom taken in consideration in most previous studies (Waqas et al., 2020). They were mostly not guided by theoretical frameworks, and only two studies guided by theoretical frameworks (Papish et al., 2013). Previous studies mainly focused on decreasing common or severe mental disorders stigma without in-depth study targeting for schizophrenia (Amsalem et al., 2020). Most studies were also lack of follow-up time, and the efficacy of the interventions in the long-term was unsure (Amsalem et al., 2020). Furthermore, interventions were traditionally conducted face to face (Amsalem et al., 2020), and this is not feasible during the Covid-19 pandemic period. But with the development of internet technology, time and social distance is no longer a problem. Thus, developing an online intervention programme to decrease the stigma towards schizophrenia will be more convenient and flexible without the restriction. Such intervention programme will be the first of its kind in mainland China.

### **Aim**

This study aims to develop a Chinese culture specific intervention to decrease schizophrenia stigma among fourth-year nursing students in mainland China. The intervention will also be assessed for its feasibility, acceptability and the preliminary efficacy in a pilot RCT study.

### **Method**

#### **Study Design**

This study consists of quantitative and qualitative research design. There are three phases of the whole study.

- 1) In the first phase, a literature review and descriptive qualitative focus group interview will be used to inform the intervention development of a pilot RCT.
- 2) The second phase will be a pilot RCT. The pilot RCT consists of three stages,

---

including the investigative learning activity (6 hours), the collaborative learning activity (4 hours), and the higher-order thinking activity (4 hours). The control group has one stage—reading a book about schizophrenia knowledge.

3) The third phase is a process evaluation to explore the barriers or facilitators of the intervention in implementation, figure out additional problems which may affect the intervention in implementation, and refine the study design for a future full power RCT.

### **Study Setting, Participants, Sampling and Sample size**

This study will be implemented in Xiang Ya Hospital, Changsha, Hu Nan province in mainland China. The participant will be fourth-year nursing students in mainland China. The first phase and third phase of focus group interviews will initially involve four participants in each focus group and the number of participants will increase until reaching data saturation. Based on the previous literature review on sample size calculations for feasibility studies, the sample size of the second phase of study was suggested between 24 and 50 (Julious, 2005; Sim & Lewis, 2012). Considering a drop-out rate of 20% reported in many psychosocial intervention studies (Van Daele, Hermans, Van Audenhove, & Van den Bergh, 2011), the total number of participants will be set at 60 (both intervention and control group will have 30 participants). Convenience sampling method will be used to recruit the participants.

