### Feasibility of Intervention

The outcome of this study will be mainly measured by the feasibility and acceptability of the intervention. Summary of the outcome measures feasibility of the intervention is shown in table 1.

Table 1 Primary Outcome of the Intervention

Primary outcome	feasibility outcomes	① Subject recruitment time ② Achievable recruitment rate ③ Eligibility rate of participants ④ The response rate of scales
	acceptability outcomes	① Drop-out rate of participants

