### **Phase 3: Process evaluation**

This phase aims to collect feedbacks from online focus group interview to explore the barriers and facilitating factors in implementing the intervention, figure out additional problems which may affect the intervention, and refine the study design for a future full power RCT.

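### Recruitment and eligibility rates are primary outcomes, but convenience sampling with no stated approach procedure makes them depend on which students the team approaches

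*Protocol*

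**What the plan says.** The Protocol section on Study Setting, Participants, Sampling and Sample size fixes both the size of the pilot and how it is filled: "the total number of participants will be set at 60 (both intervention and control group will have 30 participants", and then "Convenience sampling method will be used to recruit the participants". The setting is a single hospital. The inclusion criteria confine entry to adult, Mandarin-speaking nursing students who have finished their courses and are on placement there. No section says by what means or in what order students are approached, and none mentions a log of those approached or screened.

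Table 1, under Feasibility of Intervention, lists five primary outcomes. Three concern recruitment: "Subject recruitment time", "Achievable recruitment rate" and "Eligibility rate of participants". None is given a numerator, denominator or start point. The other two, response to the scales and drop-out, are naturally counted among enrolled participants and are not affected by this point.

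On later use, Phase 3 is meant to "refine the study design for a future full power RCT", and the section on implications hopes the study will guide later full-power trials.

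**The concern.** Convenience sampling is an ordinary way to fill a small pilot. The difficulty here is that the recruitment process is itself a primary result. A recruitment rate describes the passage from a source group to enrolled participants. If the planned number of recruits is 60 and the number approached is left open, the rate is set largely by whom the team chooses to ask. A reader planning the next trial could not tell whether a high rate reflects the hospital's students or a selective approach, and could not repeat the procedure.

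A statistical analysis plan could later supply numerators and denominators. It could not recover students who were never listed or invited. The sampling method is a protocol decision and has to be settled before enrolment.

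**Working it through.** **1. The plan's own figure.** The stated pilot range is 24 to 50 ("the sample size of the second phase of study was suggested between 24 and 50") and the stated drop-out is 20%. The total reproduces as 50 × (1 + 0.20) = 60. Dividing instead gives 50 / 0.80 = 62.5, or 63, while 48 / 0.80 = 60, and 48 lies inside the range. Nothing here turns on which route was taken; 60 is simply the planned numerator.

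**2. Recruitment rate for different numbers approached.** Rate = 60 / A, where A is the number of students approached. The protocol does not give A, so the values below are assumed. Intervals are Wilson 95%.

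| A (assumed) | 60 / A | 95% interval |
|---|---|---|
| 65 | 92.3% | 83.2 to 96.7 |
| 80 | 75.0% | 64.5 to 83.2 |
| 100 | 60.0% | 50.2 to 69.1 |
| 120 | 50.0% | 41.2 to 58.8 |
| 200 | 30.0% | 24.1 to 36.7 |
| 300 | 20.0% | 15.9 to 24.9 |

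Over this range the choice of A matters more than sampling error: the intervals at 65 and 200 are far apart. A confidence interval around the reported rate would not reveal the problem.

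**3. How the approach could move A.** Suppose, again by assumption, that keen students consent at 80% and others at 30%, and that a share k of those approached are keen. The rate is p = 0.80k + 0.30(1 − k), and A = 60 / p.
- k = 1: p = 0.80, A = 75
- k = 0.5: p = 0.55, A = 109
- k = 0: p = 0.30, A = 200

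Every student counted here was actually asked, so the three rates measure the same quantity. They differ only in who was asked, which the protocol leaves open.

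**4. Consequence for planning.** For an assumed later trial of 300 students, the number to approach is 300 / p: 375 at 0.80, 546 at 0.55 and 1,000 at 0.30. The protocol gives no size for that trial, so these figures show sensitivity and are not forecasts.

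**5. The other two recruitment outcomes.** The eligibility rate is eligible students divided by screened students. Its denominator also depends on whom the team screens, but most of the criteria are objective, so the dependence is weaker and no direction can be inferred. Recruitment time has no denominator. It depends on the target of 60 and on how hard and how widely the team recruits, which is not described.

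**The case against.** The strongest reply is that the protocol does define a bounded source group: students of one year, on placement at one named hospital, meeting listed criteria. That is right. What is missing is the route from that group to the 60, not the group itself.

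A reader might infer that the team will hand-pick the easiest contacts, stop at 60 and so report a rate that is too high. The documents do not say this. They set the total at 60 and name convenience sampling, which could equally mean an open advertisement or taking all available volunteers. Upward bias is plausible if easy-to-reach students are also more willing, but it is not established.

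A reader might also infer that the rates cannot inform the full RCT at all. That does not follow. If everyone approached were logged, the rates would be valid for that approach at that hospital and could inform a trial recruiting in the same way. The protocol does not say how the later trial would recruit. The aim of refining that trial's design is stated for the process evaluation, not for these rates in particular. What stands against the plan is that it secures neither a log nor a described approach, so even this limited use is not assured.

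A percentage obtained by dividing 60 by a whole roster should not be set beside consent among those approached. If enrolment is capped, the former is only a floor. Finally, a single mass invitation makes recruitment time describe one mailing. That is a real limitation, but the figure would then have a known meaning.

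**Conclusion.** The point holds in a limited form and is worth acting on before enrolment. Two of the five primary outcomes, the recruitment rate and to a lesser degree the eligibility rate, depend on an approach procedure that the protocol does not describe, which limits their value for planning. Recruitment time depends on the same undefined effort. The size cannot be stated from the documents: the span from 92% to 20% follows only from assuming 65 to 300 students approached. The conclusion rests on the protocol alone. Detailed rate definitions may sit in an analysis plan that is not shown, but the sampling method is fixed here.

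**What to change.** In the section on Study Setting, Participants, Sampling and Sample size, replace convenience sampling with an invitation to all fourth-year nursing students on placement at the hospital during a stated recruitment window. If no complete roster is available, log every student approached.

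Then, for the outcomes in Table 1:
- Report the numbers invited, replied, screened, eligible, consented and randomised.
- Use invited students as the denominator of the recruitment rate and screened students as the denominator of the eligibility rate.
- Measure recruitment time from first invitation to the 60th consent, and state the length of the reply window, since the time will partly reflect it.
- If more than 60 eligible students volunteer, take them in random order and count the surplus s as recruitable. The rate is then (60 + s) / invited, and the cap does not lower it.

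The cost is a roster from the hospital, assumed obtainable, plus a bulk message and a simple count at each step. The reported recruitment rate may be lower than under convenience sampling.

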### **Inclusion criteria of participants are those:**

- Participants should be 18 years old or above.
- Participants should complete all the school courses to ensure that they have similar theoretical knowledge in psychiatric nursing.
- Participants can communicate in Mandarin.
- Participants are voluntarily participating in this study.
- Participants have not participated in any other similar intervention before.
- Participants are doing a clinical practicum in Xiangya Hospital, Changsha, Hunan Province.

### **Exclusion criteria are those:**

- Participants are receiving treatment of schizophrenia or other mental illness.
- Participants are lack of essential equipment to take an online interview.
- Regular personal contact with someone with schizophrenia or other mental illness (more than three times a month). Because people's prejudice may decrease when they meet and interact with people with mental illness.

## **Procedures**

### **Phase 1: Pre-intervention qualitative study**

---

The first phase study aims to explore the knowledge, attitude, empathy, and intention behavior towards people with schizophrenia among nursing students through online focus group interview which is essential for developing an intervention programme.

### **Phase 2: Pilot intervention study**

It involves the implementation of this study intervention based on the literature review, findings of phase one focus group interview and transformative learning theory (Dincer & Inangil, 2021; Tsimane & Downing, 2020). A feasibility study using a pilot randomized controlled trial design will assess the preliminary effect of the intervention on knowledge, attitude, empathy, and intention behavior of the fourth-year nursing students towards people with schizophrenia. The research outcome will be measured at three time points: Baseline (T0), after the intervention (T1), three months post-intervention (T2).

R software will be used to generate a randomization table in this study. To decrease the potential selection bias, allocation concealment will be applied to ensure there is no prior knowledge for group assignment (Suresh, 2011). A postgraduate student will be invited to help us generate the randomization table by R software. The participants' group belonging will be determined after the participants have signed the consent form.

The intervention programme will include investigative, collaborative, higher-order thinking, and interactive learning activities. For investigative learning activities, nursing students will be encouraged to access information through evidence-based research to discover the information by themselves and which will last about 6 hours.

The collaborative learning activities will include people recovered from schizophrenia to share their experiences throughout the treatment and recovery period with nursing students who will be encouraged to raise their questions. Nursing student will create scenario-based simulation and take roles in it. The contact activity will be held through online interviews. These collaborative learning activities will last about 4 hours.

The higher-order thinking activities will include nursing students' self-criticism after scenario-based simulation, nursing students will be asked to write their opinions about schizophrenia and people with schizophrenia. Nursing students will prepare concept maps for the problems a person with schizophrenia in daily life encounter and the corresponding solutions. The higher-order thinking activities are also held online and will last about 4 hours. Nursing students will interactively take part in the above-mentioned activities, which belong to interactive learning activities.

### **Blinding**

This research is an open-label study due to the practical impossibility of blinding participants and the self-completed measures. Some strategies for minimizing allocation and assessor bias will be implemented. To minimize allocation bias, the assistant who performed randomization will be blinded. To minimize the assessor bias,

the research assistants who collected and entered the data for analysis in this study will be blinded. They were concealed of group allocation and not notified what the group labels (group 1 and groups 2) mean.

### Feasibility of Intervention

The outcome of this study will be mainly measured by the feasibility and acceptability of the intervention. Summary of the outcome measures feasibility of the intervention is shown in table 1.

Table 1 Primary Outcome of the Intervention

Primary outcome	feasibility outcomes	① Subject recruitment time ② Achievable recruitment rate ③ Eligibility rate of participants ④ The response rate of scales
	acceptability outcomes	① Drop-out rate of participants

### Preliminary Efficacy of the Intervention

We will assess the intervention efficacy at baseline, post intervention, and at three-month follow-up, including the participants' change in knowledge, attitude, intention behavior, and empathy. The self-assessment questionnaires will include as following:

1) Basic socio-demographic data will be gathered, and which will include information like age, gender, marital status, ethnic groups, university, province, religion, average family income per year, friends or family members with mental illness problems, mental illness history, whether they had contact with people with schizophrenia in the past, and whether they participated in any similar research before.

2) Knowledge about Schizophrenia Test (KAST)-Chinese version will be used to measure the stigma-related schizophrenia knowledge of participants. KAST, including 18 items, demonstrate an acceptable reliability coefficient of 0.68. The content validity index of items (I-CVI) ranged from 0.83 to 1.00, while the S-CVI/UA and S-CVI/Ave were 0.83 and 0.97, respectively, and known-group validity was satisfactory (Zhou et al., 2020).

3) Mental Illness Clinicians' Attitudes Scale (MICA)- Chinese version (Kassam, Glozier, Leese, Henderson, & Thornicroft, 2010; Li et al., 2014) will be used to measure stigma-related mental illness attitude of participants. MICA is a six-point scale that includes 16 items, and response options are from 1=totally agree to 6=totally disagree. The total score range is taken from 16-96. A lower score indicates participants having a positive attitude towards mental illness. The internal consistency is 0.72-0.75, and test-retest reliability is 0.76-0.87 of MICA in the Chinese version (Li et al., 2014; Pan Shengmao et al., 2013).

4) Reported and Intended Behavior Scale (RIBS)-Chinese version (Li et al., 2014) will be used to measure the stigma-related mental illness behavior of participants. RIBS is a five-point scale that includes eight items, and response options are designed as 1=totally disagree, 2=disagree, 3=do not know, 4=agree, 5=totally agree. The total score range is taken from 4-20 of items 5-8. The higher score

---

indicates the participants are more willing to contact people who have a mental illness. The internal consistency is 0.82, and test-retest reliability is 0.68 of RIBS in the Chinese version.

5) Jefferson Scale of Empathy-Health Profession Students (JSE-HPS)-Chinese version (Hsiao et al., 2012) will be used to measure the nursing students' empathy towards people with schizophrenia. S-JSE-HPS is a seven-point scale that includes twenty items, and response options are designed as 1=totally disagree to 7= totally agree. The total score range is taken from 20-140. The higher score indicates the participants have greater empathic attitudes. The internal consistency is 0.93, and test-retest reliability is 0.92 of JSE-HPS in the Chinese version.

### **Intervention Fidelity**

A fidelity checklist will be used to assess the intervention fidelity (Borrelli et al., 2005). All sessions will be videotaped and rated independently by a research assistant. The assessor of the checklist will be an independent research assistant, who will be trained to use the checklist to assess the intervention fidelity.

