### Appendix 8 Fidelity checklist

Treatment fidelity strategies	present	absent but should be present	not applicable
Treatment design			
1. Provided information about treatment dose in the intervention condition			
Length of contact session(s)			
Number of contacts			
Content of treatment			
Duration of contact over time			
2. Provided information about treatment dose in the comparison condition			
Length of contact session(s)			
Number of contacts			
Content of treatment			
Duration of contact over time			
3. Mention of provider credentials			
4. Mention of a theoretical model or clinical guidelines on which the intervention is based			
Training providers			
1. Description of how providers were trained			
2. Standardized provider training			
3. Measured provider skill acquisition post-training			
4. Described how provider skills maintained over time			
Delivery of treatment			
1. Included method to ensure that the content of the intervention was being delivered			

as specified (e.g., treatment manual, checklist, computer program)			
2 . Included method to ensure that the dose of the intervention was being delivered as specified (e.g., records number of contact minutes.			
3. Included mechanism to assess if the provider actually adhered to the intervention plan (applies to human providers only?) (e.g., audiotape, observation, self-report of provider, exit interview with participant)			
4. Assessed nonspecific treatment effects			
5. Used treatment manual			
Receipt of treatment			
1. Assessed subject comprehension of the intervention during the intervention period			
2. Included a strategy to improve subject comprehension of the intervention above and beyond what is included in the intervention			
3. Assessed subject's ability to perform the intervention skills during the intervention period			
4. Included a strategy to improve subject performance of intervention skills during the intervention period			
Enactment of treatment skills			
1. Assessed subject performance of the intervention skills assessed in settings in which the intervention might be applied			
2. Assessed strategy to improve subject performance of the intervention skills in settings in which the intervention might be applied			

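### The fidelity checklist assigned to the videotaped sessions is largely a study-level tool, and none of its 19 items records whether a planned activity or its planned minutes were delivered

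*Protocol*

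**What the plan says.** The Intervention Fidelity section of the Protocol fixes three things.

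- The tool: "A fidelity checklist will be used to assess the intervention fidelity". The checklist is in Appendix 8, and no other fidelity form appears in the document.
- The unit rated: "All sessions will be videotaped and rated independently by a research assistant".
- The rater: "The assessor of the checklist will be an independent research assistant, who will be trained to use the checklist to assess the intervention fidelity".

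Appendix 8 has five blocks of items. Each item is marked as present, as "absent but should be present", or as not applicable. Typical entries in the design block are "Mention of provider credentials" and "Mention of a theoretical model or clinical guidelines on which the intervention is based".

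The programme to which this applies is set out in Study Design, "including the investigative learning activity (6 hours), the collaborative learning activity (4 hours), and the higher-order thinking activity (4 hours", and by week in Appendix 1. In the investigative part, students are to "access information through evidence-based research to discover the information by themselves". The control arm is given a book to read within a month.

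**The concern.** A rater watching a session can report what was done, for how long and with whom. Appendix 8 mostly asks something else: whether the study specified, described or put in place certain features. The tool therefore does not fit the unit it is meant to rate.

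The pilot is meant to assess feasibility and to refine the design of a full trial. If sessions are shortened or activities left out, the planned ratings need not show it. The investigators would then have no structured record of how much of the programme was delivered, either when describing feasibility or when interpreting the preliminary efficacy results.

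**Working it through.** No statistical formula applies. The check is a count and a reading of the items.

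**Step 1. Count the items (Appendix 8).** Design 4 + training 4 + delivery 5 + receipt 4 + enactment 2 = 19 numbered items. Two of the design items also carry four sub-lines each (session length, number of contacts, content, duration), one set per arm: 2 × 4 = 8 sub-lines.

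**Step 2. Ask what a mark of present would record.**

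- *Design and training (4 + 4 = 8 of 19, 42%).* These cover stated dose, provider credentials, theoretical basis, and how providers were trained and kept in practice. They are properties of the study, so a tape of one session cannot change the answers.
- *The 8 sub-lines.* They name session length and content, which looks promising. However, they sit under the two items asking whether dose information was provided for each arm. As placed, they record that the information was given, not that the dose was.
- *Delivery items 1 to 3.* These concern content, dose and provider adherence. Each asks whether a method or mechanism to secure or assess them was included. Recorded contact minutes appear in item 2 only as an example of such a method. Item 3 lists audiotape and observation among its examples, so the act of taping could earn a mark of present whatever the tape shows.
- *Delivery items 4 and 5.* Item 4 asks whether nonspecific effects were assessed. Item 5 asks whether a treatment manual was used. A rater might see item 5 on a tape, but it does not show which activities or minutes were covered.
- *Receipt (4) and enactment (2).* These ask whether comprehension and skills were assessed or supported. Some could be seen on tape and could differ between sessions. They record that an assessment or strategy took place, not which planned activities were delivered.

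**Step 3. Compare with Appendix 1.** The planned content is seven search topics and a sharing activity in week one, interviews with people who have recovered and sharing in week two, simulation and sharing in week three, and self-criticism, written opinions, discussion and concept maps in week four. The number of the 19 items that record delivery of any of these, or minutes delivered, or attendance, is 0. The response scale has no field for amount.

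**Step 4. Look at what is not a session.** The stated hours are 6 + 4 + 4 = 14. The 6-hour investigative component includes searching that students do on their own, and the control arm reads a book. The Protocol states no log or completion check for either. Week one also has a sharing activity that could be taped, but its length is not given. The share of the 14 hours that video would cover therefore cannot be calculated.

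**Step 5. Check that planned minutes can be read off the plan.** Hours are given by component, not by activity. For week one, Appendix 1 allots one hour per two topics, and 7 topics ÷ 2 = 3.5 hours. It also asks for two hours every two days. Assuming this runs for one week, that is 3 or 4 occasions × 2 = 6 to 8 hours. The stated figure is 6 hours. These passages need to be reconciled before planned and actual time can be compared.

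**The case against.** The best case for the plan has four parts.

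1. *The checklist is not wholly study-level.* This stands. A reader might infer that every item has the same answer for every session. The documents support that only for the 8 design and training items. Several of the other 11, such as use of a manual or assessment of comprehension, could differ between sessions and be seen on tape. Content and dose are also the subject of delivery items 1 and 2. What remains is that these items record whether a procedure existed, not what was delivered.
2. *Video may cover much of the programme.* A reader might infer a ceiling of 8 of 14 hours (57%) by treating all 6 investigative hours (43%) as unrecordable. That does not hold, because the week-one sharing activity is of unstated length and the Protocol says the online intervention runs by video conference. Nor does leaving private searching unfilmed break a promise to tape sessions.
3. *Fidelity is secondary.* This stands. Table 1 lists recruitment time, recruitment rate, eligibility rate, scale response rate and drop-out rate. The quantitative analysis uses no fidelity score, and the comparison of the arms as randomised does not need one.
4. *Other sources exist.* This stands in part. The focus groups in phase 3 ask about ease, time cost, frequency and duration, and the recordings themselves will exist. But the focus groups collect opinions rather than a record of delivery, and the recordings help only if they are rated on a form that asks about delivery.

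**Conclusion.** The mismatch is real and limited in reach. The Protocol names the tool, the unit and the rater, so this is not a detail left to a later analysis plan. In size, 0 of 19 numbered items records delivery of a planned activity or its minutes, and at least 8 of 19 cannot vary by session. Followed as written, the checklist could be marked present throughout while planned content was skipped. The ratings therefore cannot show how far the programme was delivered, which weakens what the pilot can say about feasibility and about refining the full trial.

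A reader might go further and infer that any null or positive result becomes uninterpretable. The documents do not support that. The efficacy results are described as preliminary, the comparison of arms as offered is unaffected, and no outcome, sample size or analysis changes. What is lost is the ability to relate a result to the amount of programme delivered.

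The conclusion rests on Appendix 8 being the only fidelity form, as shown in the Protocol, and on reading its items as worded. It agrees with the reference list, where the title of the cited source describes a tool used to evaluate fidelity over a decade of health-behaviour research. This is an inexpensive improvement, not a flaw that threatens the trial.

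**What to change.** 1. Keep Appendix 8 and complete it once, as a study-level check.
2. Have the same trained assistant rate the existing videos on a one-page session form built from Appendix 1. For each planned activity it should record delivered yes, partly or no, planned and actual minutes, and attendance.
3. Before the form is finalised, reconcile the week-one time statements and divide the stated component hours among the activities, so that planned minutes are defined.
4. Add a brief participant log of time or completion for the self-directed searching and for the control-arm reading.
5. Report, by week, the percentage of planned components and of planned minutes delivered.

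The cost is one form, one short log, slightly more rating work and a little more participant reporting. The assistant and the recordings are already in the plan.
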